8. BUDGET REQUIREMENT WITH DETAILED ITEM-WISE BREAK-UP AND FULL JUSTIFICATION

As the study is a prospective observational study of MSF's comprehensive package of care currently being provided for people living with HIV / AIDS within Manipur, minimal additional costs outside of MSF's normal operational costs will be required.

There will be no requirement for additional funding from NACO

A. BUDGET FOR PERSONNEL: Nil budget requirement

Justification:

The coordinating team at Delhi will be responsible for the preparatory activities, training, conduct of meetings and monitoring of the study. They would be responsible for coordinating the research activities, data management and report writing.

The investigators appointed at the site will enroll the participants, collect data, organize local meetings, follow-up cases and conduct the study activities at each site in conjunction with the coordination team.

All of the coordinating staff and field staff, who will be involved in the conduct of this study, are currently full time employees of MSF OCA India responsible for the conduct of MSF's routine programmatic care and treatment activities. There will be no further additional staff requirements for the conduct of this study.

B. BUDGET FOR MEETINGS AND TRAININGS: Nil budget requirement

Justification:

All of protocols, tools, IEC material and counselling materials have been developed by current members of the coordinating and field teams to support routine programmatic activities. Similarly trainings have been delivered in study sites by coordinating team members and senior field team members to support routine programmatic activities. Additional trainings for team members involved in the conduct of the study have been incorporated into the routine field trainings.

C. BUDGET FOR CONSUMABLE MATERIALS: Total requirement: 1,00,000 Rs

Table 5: Proposed budget for consumables

Printer Toners, Software, Stationeries including printing of forms and IEC material	BUDGET (In Rupees)			
	Year 1	Year 2	Year 3	Total
For two sites	50000 (25,000 for each site)	50000 (25,000 for each site)	50000 (25,000 for each site)	1,50,000

Justification:

Budget for printing of informed consent and data collection forms, IEC material and Counseling flip charts and other essential stationeries needed for functioning of the project.

D. BUDGET FOR TRAVEL: Nil budget requirement

Justification:

The coordinating team in Delhi regularly conducts supervisory visits to the sites to monitor the conduct and quality of our routine care and treatment activities. The regular monitoring of the study conduct and data collection will be incorporated into these routine visits. The field team including the LRI co-investigator lives within the area of the study sites and as such no additional travel costs will be incurred.

The Principle investigator and coordinating team are located within Delhi and such no travel costs will be incurred for the conduct of required meetings with NACO during the course of the study.

E. BUDGET FOR OTHER COSTS: **Total requirement : 2,50,000 Rs**

Table 6: Proposed budget for dissemination costs

Item wise by category	BUDGET (In Rupees)			
	Year 1	Year 2	Year 3	Total
Printing of report and research brief			50,000	50,000
Dissemination of study findings			1,00,000	1,00,000
Publication or by presenting data in Conferences and Seminars on the subject			1,00,000	1,00,000
total	Nil	Nil	2,50,000	2,50,000

Justification:

This budget involves cost towards developing and printing of the final report, the draft of which would be shared with the investigators and coordinators of the study. For dissemination of information in the scientific community, the data will be presented in workshop attended by collaborators, researchers, policy makers, programme managers and PLHA group representatives. Cost that would be incurred by investigators to attend conferences/seminars or publish the manuscript based on data collected is budgeted under this head.

TOTAL COSTS FOR LRI

Table 7: Proposed total budget

Item wise by category	BUDGET (In Rupees)			
	Year 1	Year 2	Year 3	Total
A	0	0	0	Nil
B	0	0	0	Nil
C	50,000	50,000	50,000	1,50,000
D	0	0	0	Nil
E	0	0	2,50,000	2,50,000
total	50,000	50,000	3,00,000	4,00,000
5% OVERHEADS	2,500	2,500	15,000	20,000
Total	52,500	52,500	3,15,000	4,20,000

REFERENCES

2. WHO. Global policy report on the prevention and control of viral hepatitis in WHO Member States. Geneva; 2013.

(Antigen S):	 Yes  No  DK →If No or DK, skip to question 140
133_Date of the test:	____ - ____ (mm-yyyy)
134_Result of the HBV tests:	 Positive  Negative  DK
NURSE:	Comorbidities (From Fuchia summary sheet in front of patient file)
HIV status:	
140_Previous HIV Tests	 Yes  No  DK → If No or DK, skip to question 160
141_Year of the last HIV test:	____ (yyyy)
142_Result of the HIV tests: HIV Status:	 Positive  Negative  Intermediate  DK →If HIV status negative, indeterminate or DK, skip to question 160
143_Is the patient followed in MSF HIV cohort?	 Yes  No  DK →If No, skip to question 146
CD4 count at HIV care enrolment	
144_Date of the CD4 count:	____ - ____ (mm-yyyy)
145_Result:	_____ cells /µL  DK
146_WHO HIV staging at HIV care enrolment)	____  DK
147_HIV Treatment:	 Yes  No  DK → If No or DK, skip to question 160
148_Date of the first received ART treatment:	____ - ____ (mm-yyyy)
149_Date of start of the current ART regimen:	____ - ____ (mm-yyyy)
150_Current HIV treatment:	 DK
Drug _____	Daily Dosage _____  DK (dosage not entered
Drug _____	Daily Dosage _____  DK in the database)
Drug _____	Daily Dosage _____  DK
Drug _____	Daily Dosage _____  DK

Patient's initials: _____ Pt file N° _____/_____ Name of interviewer: _____	Data clerk Initials: _____ Date data entry: ____ - ____ - ____ (dd-mm-yyyy)
--	--

DOCTOR: Does the patient have one of these comorbidities? (Patient's file or interview)				
160_Current Tuberculosis	 Yes	 No	 DK	
161_History of sickle cell or thalassemia	 Yes	 No	 DK	
162_Flukes (Site)	 Yes	 No	 DK	
163_Renal impairment	 Yes on Dialysis	 Yes not on Dialysis	 No	 DK
164_Diabetes	 Yes IDDM	 Yes NIDDM	 No	 DK

DOCTOR: Risk factors of liver complications (present or past) or reinfection (Patient's interview)				
Does/ Did the patient have one or several of these risk factors:				
170_History of Invasive medical procedures (surgery, biopsy, endoscopy...)	 Yes	 No	 DK	
171_History of blood transfusion	 Yes	 No	 DK	
172_Health care worker (current or past)	 Yes	 No	 DK	
173_Prisoner	 Current	 Past	 No	 DK
174_Partner with HCV positive status	 Current	 Past	 No	 DK

CRF1: To be filled by the Counsellor

Pt file N° _____/_____ Name of interviewer: _____ Date of interview: _____	Data clerk Initials: _____ Date data entry: ____ - ____ - ____ (dd-mm-yyyy)
--	--

To evaluate the risk of depression of the patient: (from PSA form) (data clerk take note of numbering)

166_Screening Depression PHQ9 Score _____ (Refer to the specific assessment tool)

Risk factors of liver complications (present or past) or reinfection (Patient's interview)

Is the patient?

175_Transgender Yes No DK

176_Man who has ever had sex with a man (MSM) Yes No DK

177_Sex worker Current Past No DK

Addiction (Patient's interview)

180_To evaluate the alcohol consumption of the patient: **AUDIT** score _____ **Refer to the specific tool**

190_Has the patient ever used any drug /substance?

Current Past No DK

→If No or DK, skip to the end of the questionnaire

Which type of drug does the patient use or have they used in the past?

191_Opioids: heroin, morphine, opium.... Current Past No DK

192_Cocaine: coke, crack... Current Past No DK

193_Amphetamine: speed, meth.... Current Past No DK

194_others Current Past No DK

195_How has the patient use the drug?

Injecting Smoking Injecting and smoking combined Others

198_Opiods consumption of the patient: Opiods **ASSIST** score _____ **Refer to the specific tool**

Is the patient attending a harm reduction program? Yes No DK

196_an opioid substitution program or oral substitution treatment (OST)

Current Past No DK

197_a syringe exchange program Current Past No DK

Appendix 2: Follow up visit form CRF2 _N° Visit: _____

CRF2 _N° Visit: _____

1_ Surname: _____	2_ Forename: _____ (not to enter in the database)
Patient's file N° _____	
3_ Identification cohort Number: _____ 4_ ID Key _____ (to be filled by data clerk)	

10_ Date of consultation: ____ - ____ - ____ (dd-mm-yyyy) 11_ Site of consultation: _____	12_ Name of interviewer: _____ 13_ Doctor / Clinical Officer / Nurse / Others	14_ Data clerk initials: _____ 15_ Date of data entry: ____ - ____ - ____ (dd-mm-yyyy)
--	--	---

Instructions: *Complete all the questions (one answer per question), considering the skips*
If the answer is unknown, tick the box DK (don't know) or use DK for missing day, month or value.

NURSE :	Follow-up (only weight to be entered in the database)
Body temp: _____[C°] Blood Pressure: ____/____ [mmHg] Pulse : ____/min O2 sat : ____ [%]	
210_ Weight: _____ (in kg)	

DOCTOR:	Medical baseline information:
Liver dysfunction at the clinical examination	
220_ Presence of ascites  None  Mild  Moderate  Severe  DK	
221_ Presence of hepatic encephalopathy  None  Grade I-II  Grade III-IV	
 DK	

Free text for consultation

DOCTOR: 241_ Other or NEW comorbidities	 Yes  No  DK	if No, skip to question 250
242_ HIV infection	 Yes  No  DK	(new test done during the current follow up)
243_ HBV infection	 Yes  No  DK	(new test done during the current follow up)
244_ Tuberculosis (new diagnosis)	 Yes  No  DK	
245_ Diabetes	 Yes  No  DK	
246_ Malaria	 Yes  No  DK	
247_ Dengue	 Yes  No  DK	
248_ Other	 Yes  No  DK	
249_ If yes: specify _____		
250_ New Test results (bio or others)	 Yes  No  DK	if Yes: To fill the Lab Form

Pt file N° _____ Visit N°: ____ Name of interviewer: _____	Data clerk Initials: _____ Date data entry: ____ - ____ - ____ (dd-mm-yyyy)
--	--

DOCTOR: HIV Care follow-up	
260_ Is the patient HIV positive	 Yes  No  DK If No or DK, skip to question 270
261_ CURRENT WHO staging (Site) _____	 DK
262_ HIV consultation outcome:	
 Pre ART (skip to 270)	 ART Initiation
 Continuation same dose/ regimen (skip to 270)	 Modification dose/regimen
 Discontinuation due to adverse event (skip to 270)	 Stop for other reasons  (skip to 270)
263_ If HIV Treatment initiation or modification, complete with name and dosage of the new regimen.	
 DK	
Drug _____	Dosage _____  DK (dosage not entered)
Drug _____	Dosage _____  DK (in the database)
Drug _____	Dosage _____  DK
Drug _____	Dosage _____  DK

DOCTOR: CONSULTATION DECISION	
270_ Is the patient eligible for the HCV treatment or currently under treatment?	
 Not assessed /pending results (skip to 280)	 Eligible /or already under treatment (skip to 272)
 Not eligible	 Follow up after treatment (skip to 280)
271_ Reasons not eligible currently for treatment (after skip to 280)	
 Due to ineligible liver stage	 Patient's unwillingness to start
 Due to liver decompensation	 Contraindication to treatment
 Pregnancy/breastfeeding	 Others: (Clinical Case Review priority)
272_ Decision for treatment or continuation of care	
 Waiting List (skip to 280)	 Initiation (skip to 274)
 Continuation same dose	 Modification dose due to weight change
 Adverse event/pregnancy leading to Modification	 or Discontinuation of treatment(+ fill CRF AE)
 Stop for other reasons (skip to 280)	 Treatment Finished (skip to 280)
273_ If under HCV treatment: How many doses have been missed for the last three days? _____  DK (dose = all pills taken at the same moment during the day)	
274_ Treatment if initiation or modification (do not fill if continuation of same regimen)	
Drug _____	Dosage _____ mg per day / per week
Drug _____	Dosage _____ mg per day / per week
Drug _____	Dosage _____ mg per day / per week

280_ End of follow up:	 Yes  No	if Yes, skip to question 290
281_ Date of the next consultation (for HCV care) ____ - ____ - ____ (dd-mm-yyyy) (go to next page)		
290_ Reasons of End of Follow up in HCV care (end of questionnaire)		
 Cured	 Transfer out	 Medical decision to stop HCV Follow up
 Death	 Loss of Follow up	

To be filled by the COUNSELLOR

Pt file N° _____	Data clerk Initials: _____
Visit N°: _____	Date data entry: ____ - ____ - ____ (dd-mm-yyyy)
Name of interviewer: _____	

COUNSELLOR:	Addiction Follow-up		
230_ Drug use since last visit	 Yes	 No	 DK
231_ Opioid substitution program (or OST)	 Yes	 No	 DK
232_ Alcohol use since last visit	 Yes	 No	 DK

COUNSELLING SESSION (Information entered in Hepa-MUD)			
300_ Counselling Focus (only one answer is possible, mark ONLY the main focus of the session)			
 Enhanced Coping			
 Enhanced Motivation			
 Practical Support			
 Family related issues			
 Adherence issues			
 Alcohol use			
 Lifestyle changes			
 Drug Use / Harm reduction			
 Mild/moderate depression			
 Other Mental Health issues			
 Regular follow-up			
 Pretreatment adherence counselling	 1	 2	 3
 DK			
 NS			
301_ Function rating score	_____ (0-10 score)	 DK	 NS
Complaint rating score (not entered into database)	_____ (0-10 score)	 DK	 NS
302_ Adherence - % of pills taken since last visit	_____	 DK	 NS
303_ PHQ-9 Score (only if PHQ-9 done at this visit)	_____ (0-27 score)	 DK	 NS
Validated Depression (score ≥5) (not entered into database)		 Yes	 No
 PSA	 Start Treatment	 End Treatment	 SVR-12
			 SOS
304_ Mental Health or psychosocial issues: _____			

Other information (Not entered in Hepa-MUD)
Remarks _____

Special attention _____

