6. DETAILED RESEARCH PLAN

METHODOLOGY

I. Study Design

The study will be a prospective longitudinal cohort study, which will monitor the diagnosis, treatment and follow-up of the HIV patients identified with a chronic hepatitis C within 3 clinic sites in Manipur; Churachandpur, Chakpikarong and Moreh.

The analysis of routinely collected clinical data will facilitate the assessment of the effectiveness of HCV treatment among patients with chronic hepatitis C, co-infected with HIV, from time of confirmation of their HCV Viral load until SVR12, death, lost to follow up, medical decision to exit the study or transfer out, whichever comes first.

The study will assess implementation of new recommended HCV-curative regimens in real world settings, not specific new drugs. The specific treatment regimens used, including new DAAs, will be selected in accordance with current WHO, international and national recommendations and protocols (18-20). Of the new DAA's, only drugs registered and available in India will be used in accordance with international and national recommendations and protocols.

II. Study population

The study population will include HIV infected patients from Manipur state diagnosed with chronic hepatitis C (viral load HCV positive) meeting eligibility criteria. These patients will be directly identified in the MSF sites.

III. Sample size

The sample will exhaustively include all patients meeting the inclusion criteria in each site for a period of two years. Currently MSF, in collaboration with NACO has approximately 1600 adult patients being actively followed up for HIV care within Manipur. The overall rate of HIV-HCV co-infection, based on HCV serological screening performed to date is approximately 27%. Assuming 80% of serologically positive patients have chronic hepatitis C, the minimum sample size expected for this study will be 345 patients.

IV. Sampling design

The sample will exhaustively include all patients meeting the inclusion criteria in each site for a period of two years.

Inclusion and Exclusion criteria:

When the results of VL tests become available, all patients over 18 years will be invited to participate in the study, if they fulfill eligibility criteria. Inclusion is not linked with eligibility for HCV or HIV *treatment*. A criterion of non-eligibility to treatment is not considered as inclusion or exclusion criteria for study participation¹.

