The individual may withdraw consent at any point during the study with no impact on treatment and care.

¹ Eligibility for study inclusion and HCV treatment are different. The study will also include HCV positive patients who do not receive treatment either due to non-priority of treatment or presence of clinical contraindications. (These patients may receive treatment at a later date). This is intended to fulfil secondary objectives 'i' and 'j'. However patients will receive standard HCV treatment and care in the event of non-eligibility to the study or refusal to participation in the study.

Table 1: Study participant eligibility criteria

	Eligibility criteria for study inclusion	Eligibility criteria for HCV treatment
Inclusion criteria	
 • HIV/HCV co infection independent of the stage of liver disease • Over 18 years of age • HCV viral load greater than 12UI/mL • HIV positive status confirmed by the national and MSF algorithm • Able and willing to provide informed consent • Willing to comply with all study procedures 	Clinical Review 
 • Confirmed HCV infection • HIV infection controlled on ART or asymptomatic HIV infection with CD4 count >500/ μL in the absence of ART • Controlled drug use • Controlled opportunistic infections • Hemoglobin threshold: 9 g/dL
		Psychosocial Review 
 • Adherent to HIV treatment and appointments • Controlled use of substances (if relevant) • No evidence of uncontrolled psychiatric disorder
Exclusion criteria	
 • Individual aged less than 18 years • Individual does not consent to be part of the study. 	Clinical Review 
 • Evidence of hepatocarcinoma • Advanced/terminal heart or pulmonary or renal or other disease • Active, uncontrolled opportunistic Infections • First 3 months of a new ART regimen (unless minor ARV change for toxicity); • Pregnancy or planning pregnancy in following months, unwillingness to use contraception Breastfeeding women.
		Psychosocial Review 
 • Unwillingness of the patient to adhere to HCV treatment & ART • Uncontrolled severe psychiatric disorder. • Unstable substance use

V. Statistical methods to be used

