The following definitions will be considered:

In case of viral load detectable 12 weeks after end of treatment, the outcome will be considered as treatment failure.

- Deaths will be recorded by the medical teams, notified by a close relative or friend or reported by a tracing team (for programs implementing such strategy).
- Loss to follow-up is defined as two months after a planned date of appointment without contact, among patients who were not dead or transferred out.
- Transfer out is defined as a patient who has been transferred to another medical facility or consultation and for whom the treatment outcome is not known, without the possibility to continue the HCV follow up in the study site. Patients that require to be transferred out will be informed that it is very unlikely that they can continue HCV treatment. In case of possible return to the study site, the patient may be proposed again to enter in the study and informed consent will be sought again. The same identification number will be used.
- Exit due to medical reason is defined as a cessation of follow decided by the clinicians, in collaboration with the patients, due to other more urgent medical needs.

Secondary endpoints:

- Proportion of patients included in the cohort by socio-demographic characteristics: age group, sex, occupation, marital status, risk factors of HCV exposition

- Proportion of patients included in the cohort by clinical and biological characteristics: genotype, HCV viral load, liver fibrosis staging, presence of ascites, HIV WHO staging at baseline, CD4 count and HIV viral load prior to HCV treatment, HBV status, Child pugh score, hematology, biochemistry
- Proportion of patients with HBV infection defined as a positive RDT with HBV AgS diagnosis
- Distribution of liver fibrosis stage among included population
- Proportion of patients with HCV treatment initiated
- Proportion of SVR 12 among the patients having completed HCV treatment.
- Proportion of patients with SVR 12 stratified by regimen and by genotype
- Proportion of patients with SVR 12 stratified by site
- Mortality among the patients in the HCV cohort overall, and among patients who initiated treatment or among patients without treatment initiation
- Proportion of defaulters during before, during and after treatment
- Proportion of patients transferred out, and for whom medical decision to interrupt HCV follow up has been taken

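### CRF2 item 290 has no code for virological failure, so a patient closed after a detectable SVR12 result may be counted as a medical exit

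*Protocol*

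**What the plan says.** - **The form (Protocol, Appendix 2, CRF2).** "290_ Reasons of End of Follow up in HCV care" is reached only when "280_ End of follow up" is answered Yes. If the answer is No, the form takes the date of the next HCV consultation. Item 290 has five boxes: cured, transfer out, "Medical decision to stop HCV Follow up", death and loss to follow-up. It has no failure, 'other' or don't-know box. The form's instruction is "Complete all the questions (one answer per question), considering the skips".
- **End of study follow-up (section 6.I, Study Design).** Patients are followed "until SVR12, death, lost to follow up, medical decision to exit the study or transfer out, whichever comes first".
- **Outcome definitions (section 6.VIII).** "In case of viral load detectable 12 weeks after end of treatment, the outcome will be considered as treatment failure". The failure definition lists detectable virus alongside death, loss to follow-up, medical exit and transfer out. Medical exit means that clinicians and patient stop follow-up because something else is medically more pressing. Loss means two months without contact after a planned appointment.
- **Secondary endpoint (section 6.VIII).** "Proportion of patients transferred out, and for whom medical decision to interrupt HCV follow up has been taken".
- **Laboratory form (Appendix 3).** Items 420 and 421 record the HCV viral load and its date. Table 3.0 schedules a viral load 12 weeks after treatment.
- **Consent (section 6.IV).** "The individual may withdraw consent at any point during the study", with no effect on care.

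**The concern.** The five boxes cover one success and four exits. Section 6.VIII describes one success and five routes to failure. The route without a box is the virological one, which is the outcome the study exists to measure.

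The form must be answered and has no residual category, so a site closing such a patient is drawn to the nearest box, a medical decision to stop. That box feeds a stated secondary endpoint, and the protocol's definition of medical exit does not include virological failure. What is at stake is whether the reported share of medical decisions means what section 6.VIII says it means.

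The gap looks like an oversight. CRF1 item 124 can code previous HCV treatment as completed without success or stopped for non-response, and CRF2 item 271 has an 'others' box.

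**Working it through.** **Step 1: compare the outcome routes with the boxes.**

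| Route in section 6.VIII | Box in item 290 |
|---|---|
| Success at SVR12 | Cured |
| Detectable viral load at 12 weeks after treatment | none |
| Death | Death |
| Loss to follow-up | Loss of follow-up |
| Medical exit | Medical decision |
| Transfer out | Transfer out |

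For a patient who attends the SVR12 visit with detectable virus and is then closed:
- *Cured* is false.
- *Loss* does not apply, because the patient attended.
- *Medical decision* is nearest in wording but does not fit its definition.

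**Step 2: who is exposed.** Only patients with item 280 = Yes reach item 290. A patient with virological failure who stays in HCV care has 280 = No and is not misfiled.

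**Step 3: effect on the primary endpoint.** All five failure routes count as failure among patients who initiated treatment. Moving a patient from the virological route to medical exit changes neither numerator nor denominator of the SVR12 proportion.

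**Step 4: possible effect on the medical-decision endpoint.** The only related figure in the protocol is the expected sample in section 6.III: 1600 × 0.27 × 0.80 = 345.6, which reproduces the stated 345. The protocol gives no failure rate, medical-exit rate or treated share, so the rest is assumed. Let

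recorded share = (M + q × V) / N,

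with N = 345 included patients, M = 3 true medical exits (3/345 = 0.9%), V virological failures, and q the fraction of failures that are both closed and ticked as a medical decision.

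At q = 0, the recorded share is the true 0.9%. At q = 1:

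| Failure rate among treated | V, all 345 treated | Recorded share | V, 241 treated (70%) | Recorded share |
|---|---|---|---|---|
| 3% | 10 | 13/345 = 3.8% | 7 | 10/345 = 2.9% |
| 5% | 17 | 20/345 = 5.8% | 12 | 15/345 = 4.3% |
| 10% | 34 | 37/345 = 10.7% | 24 | 27/345 = 7.8% |
| 15% | 52 | 55/345 = 15.9% | 36 | 39/345 = 11.3% |

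The excess over the truth is q × V/N. It lies between zero and the full virological failure proportion V/N. Nothing in the protocol fixes q.

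**The case against.** The case against has four parts.

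1. **A reader might infer that every virological failure has to be misfiled.** The documents do not support this. Item 290 concerns HCV care, not study participation, and the forms are routine clinical forms already in use (section 6.VI). The plasma-storage text in section 6.VII foresees further tests and a change of care after failure. Item 280 = No is correct for a patient who stays in care. This stands, and it limits the point to failures whose HCV follow-up is closed.

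2. **A reader might infer that the exit endpoints are corrupted and the failures lost.** This too goes beyond the documents. The dated viral load on the laboratory form lets an analyst separate SVR12 failures from true medical exits. The protocol also does not say that the exit endpoints are read from item 290 alone, and a SAP may set the derivation. This stands as far as an SVR12 result exists. However, item 290 is the only item shown that records why HCV follow-up ended, and the protocol states no reconciliation with the laboratory form. For a patient closed before SVR12, a viral load alone does not give the reason.

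3. **Failures might be said to drift into loss to follow-up.** That is weak. Loss requires two months without contact, and HCV visits are integrated with HIV clinic visits.

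4. **A reader might infer that withdrawn consent needs a code in item 290, and that withdrawn patients have no outcome in the primary analysis.** Withdrawal does not end HCV care, so item 290 is the wrong place for it. How such patients count is detail that a SAP commonly settles. The visible part of CRF1 starts at item 120, so it cannot be shown that no form records withdrawal. What remains is that item 21, quoted in section 6.VI, records only whether consent was signed, and no item shown records withdrawal or its date.

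**Conclusion.** The point holds in limited form. Item 290 lacks a code for virological failure and has no residual box, although the form demands an answer and section 6.VIII makes detectable virus a separate failure route. A patient closed after a detectable SVR12 result may be recorded as a medical decision, contrary to that section's definition, and this can inflate the secondary endpoint on medical decisions.

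The size is unknown. Inflation is zero if failures stay in HCV care or are separated by laboratory result. It reaches the full virological failure proportion if all are closed and misfiled. The upper-bound figures of 2.9% to 15.9% against a true 0.9% rest on assumed failure rates of 3% to 15%, 70% or 100% treated, three true medical exits, a denominator of all 345 included patients, and every failure misfiled. They illustrate the range and do not predict a result.

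The primary SVR12 proportion does not change. This is a cheap improvement to a descriptive secondary endpoint.

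**What to change.** - Add two boxes to item 290: *Treatment failure (HCV RNA detectable at 12 weeks after end of treatment)* and *Other, specify*.
- Before computing the exit endpoints, cross-check item 290 against the dated viral load in items 420/421, using the success threshold in section 6.VIII (undetectable or below 12 IU/mL). Query any patient filed as a medical decision who has a viral load above that threshold at SVR12, and any patient filed as cured without a qualifying result.
- Record withdrawal of study consent, with its date, as a separate item outside item 290, so that study status and care status stay distinct.

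The main change costs two tick boxes and one database check on a form already in use. The withdrawal item adds one dated field. No visit, test or clinical rule changes.
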